## **Appendix E: Proposed Data Structure to be Shared by Sites with Westat**

Based on conversations with participating collaborating sites, study sites would prefer to pre-process individual-level records for each seasonal cohort and then share the cohort datasets with Westat & CDC. The proposed data structure would be one data package for each influenza season. For the primary objectives, data packages would be created for each season going back as early as the 2010–2011 season through the 2018–2019 influenza season. For secondary objectives, data packages would be created for the 2019–2020 influenza season and contemporary season, depending on whether the prospective data capture objective is exercised.

[figure not shown]
Each seasonal data package would include data as specified in Appendix B. Sites would be responsible for deriving data elements using the definitions from Appendix B and doing so prior to sending data to Westat.

Example 3: Pre-processed (by the study site) individual-level records for cohort are shared with Westat & CDC

\*For influenza and other vaccinations received dating back to 2010, where possible.  
 †For influenza season of interest.

Example 3: Pre-processed (by the study site) individual-level records for cohort are shared with Westat & CDC

\*For influenza and other vaccinations received dating back to 2010, where possible.  
 †For influenza season of interest.

## **Appendix F: Data Management Plan**

See accompanying document “Data Management Plan.”

## Appendix G: Suggestions for Site Data Validations using Primary Health Records

To ensure that extracted data reflect the underlying data from the primary health records, several validation steps are being requested, including review of a limited number of primary records. Below are suggestions for how many health records to review, how to stratify the sample that are reviewed, and how to report the results of the review.

- Perform primary record review on a minimum number of medical charts and compare the information in the primary record to the information captured through data extraction:
  - If data extraction methods or data storage platforms have changed during the study period, perform data validations for records from before and after the date when the change occurred.
  - If multiple health organizations contribute data to the site, perform data validations for each of the contributing organizations with differing data extraction methods or data storage platforms.
- A minimum number of charts should be reviewed for each of the following groups:
  - Unvaccinated for influenza (per registry, EMR or billing data)
  - Vaccinated for influenza (per registry, EMR or billing data)
  - Tested for influenza (per EMR or laboratory data stream)
  - Not tested for influenza (per EMR or laboratory data stream)

Sites who have participated in multi-site vaccination studies and have validation data from those studies can omit the unvaccinated and vaccinated groups from the primary record review.

- At a minimum for each of the 4 strata, above, 20 charts should be reviewed — for a total of 80 charts.
  - If sites are conducting chart reviews from multiple hospitals or health systems or organizations because of differences in data streams, data extraction methods, or data storage platforms, then the minimum number of chart reviews per group can be 10.
  - For example, if the site consists of 3 health systems/organizations, then chart reviews should be done for each of the health systems. If 10 charts are reviewed per group in a health system, then 40 total charts will be reviewed for each health system. Across 3 health systems, the total minimum number of charts would be 120.
- For each group, randomly sample among children and adults (e.g. vaccine records for 10 unvaccinated children, 10 records for unvaccinated adults, 10 records for vaccinated children, and 10 records for vaccinated adults).
- For those tested and not tested for influenza, randomly sample among children and adults with outpatient encounters and children and adults with inpatient admissions (e.g. 5 charts for children seen in the outpatient setting who were tested for influenza, 5 charts for children in the inpatient setting who were tested for influenza, 5 charts for children

seen in the outpatient setting who were not tested for influenza, 5 charts for children in the inpatient setting that were not tested for influenza, and the same pattern among adults).

- Validate data using known cohort members from relevant influenza seasons. We will not require that validations be performed on all study seasons, however sites should perform validation on seasons that are representative of the typical data extraction and data storage structure for the entire study.
- Validate against the following data elements at a minimum (more if needed)
  - Vaccination status
  - Influenza testing done and test results, if testing was done
  - Death
  - ICU admission
  - Mechanical ventilation
- Sites will not be required to review a minimum number of charts per data element or to achieve a certain percentage concordance between data obtained from data pull vs chart review.
- Use your best judgement to decide whether additional charts need to be reviewed or additional review of the EMR data pull programming needs to take place based on results
- Summarize results from validation in tables; examples of Tables 1 and 2 are below. Include additional tables for each season/period or site that undergoes validation.

**TABLE 1. Characteristics of charts pulled for validation.**

| Study season:                                       |                          |
|--|--------------------------|
| Characteristic                                      | Charts pulled (n) |
| Pediatric outpatient encounters                            |                          |
| Adult outpatient encounters                                |                          |
| Pediatric inpatient admission                              |                          |
| Adult inpatient admissions                                 |                          |
| Among charts pulled for inpatient admissions, number with: |                          |
| ICU admission  |                          |
| Mechanical ventilation                                     |                          |
| In-hospital death  |                          |

**TABLE 2. Concordance between chart review and data pull.**

| Data Element    | Cases Reviewed (n) | Percent Agreement with chart (n, %) | Notes |
|------------------------|---------------------------|--|--------------|
| Influenza vaccination  |                           |  |              |
| Influenza testing done |                           |  |              |
| Influenza test result  |                           |  |              |
| ICU admission          |                           |  |              |
| Mechanical ventilation |                           |  |              |
| In-hospital death      |                           |  |              |

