### 4.1 Primary Objectives

1. Assess the validity and biases associated with defining the source population based on care-seeking.
  - Compare characteristics of the different cohorts, as defined above, assessing differences in the demographics, the frequency of underlying high-risk conditions, and the frequency of respiratory hospitalizations during influenza season.
2. Assess internal and external validity of influenza vaccination data for current and prior seasons.
  - Internal validity:
    - Assess the accuracy of the derived vaccine status variable in relation to a manual review of records on a subset of the cohort.
    - Describe the contributions to the overall conclusion about vaccination status by various sources from which vaccination data were obtained.
    - Describe the consistency of vaccination data that are available by data source, including date of vaccination, vaccine type, vaccine route, vaccine

lot number, setting in which vaccine was administered, number of doses of vaccine (children <9 years).

- Describe completeness of vaccination data (e.g. date of vaccination, type of vaccine, lot number) by data source for the current season and prior seasons.

- External validity:

- Compare vaccine coverage and data completeness to values reported from other studies with active enrollment / prospective data collection.

3. Assess biases associated with clinical testing for influenza and other respiratory viruses and whether they differ in the inpatient versus outpatient setting:

- Assess the accuracy of the extracted test dates, types, and results in relation to a manual review of records on a subset of the cohort.
- Estimate proportion of cohort enrollees tested for influenza and other respiratory viruses during the influenza season.
- Describe types of influenza and other respiratory virus tests performed on cohort enrollees by pediatric and adult age groups and how test types vary by setting.
- Estimate the proportion of respiratory hospitalizations tested for influenza during the influenza season and factors associated with influenza testing in the inpatient setting including age, high-risk conditions, current season influenza vaccination status, ICU stay, timing of encounter within season, diagnoses codes.

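### Appendix G samples charts by extracted status, but its example Table 2 pools them into one percent agreement that cannot show whether the extraction misses or invents records

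*Protocol*

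**What the plan says.** Appendix G asks sites to compare extracted data with primary records. It defines four groups, under the instruction "A minimum number of charts should be reviewed for each of the following groups": unvaccinated, vaccinated, tested and not tested. Membership follows the extracted value and not the chart, for example "Not tested for influenza (per EMR or laboratory data stream". The quota is equal across groups: "At a minimum for each of the 4 strata, above, 20 charts should be reviewed", 80 charts in all. Where a site covers several organizations the quota can fall to 10 per group, and the worked example ends "Across 3 health systems, the total minimum number of charts would be 120".

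All four groups are split by age ("For each group, randomly sample among children and adults"). Only the two testing groups are also split by setting ("randomly sample among children and adults with outpatient encounters and children and adults with inpatient admissions"); the example uses 5 charts per cell.

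For reporting, Table 1 counts charts by age and setting, and counts ICU stays, ventilation and deaths. Table 2 has one row per data element, with the number of cases reviewed, one column headed "Percent Agreement with chart (n" and a notes column. Both tables are offered as examples. Further tables are requested by season, period or site, but not by extracted status, age or setting.

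The results serve Section 4.1. Objective 2 asks how accurate the derived vaccine status is against manual review. Objective 3 asks the same of extracted test dates, types and results, under a heading that asks about testing biases and "whether they differ in the inpatient versus outpatient setting".

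**The concern.** When charts are sampled on the extracted value, agreement among those extracted as tested is a positive predictive value, and agreement among those extracted as not tested is a negative predictive value. The two answer different questions. To describe the cohort they must be weighted by how common each group is there. Table 2 as drawn merges them, and the weights are then those of the quota, half and half, whatever the real split. Vaccination has the same structure.

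Two things are lost. One is accuracy in the cohort: sensitivity, specificity, or even agreement at the right weights. The other is direction. An extraction that misses tests or doses lowers the proportion tested, coverage and incidence; one that records false ones raises them. The same printed percentage is compatible with either. Appendix G sets no concordance threshold and leaves further review to judgement on the results, so the person judging needs to see which error is present.

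The text also does not say which charts feed each row. If all 80 charts are scored on every element, the vaccination row mixes charts drawn on vaccination with charts drawn on testing.

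**Working it through.** **Stated totals.** 4 groups × 20 = 80 charts, and 3 systems × 4 groups × 10 = 120; both match Appendix G. The testing example is 8 cells × 5 = 40 charts, which equals the two testing groups. The protocol states no agreement or sensitivity figure to reproduce.

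**Inputs**
- 20 charts extracted as tested and 20 as not tested (Appendix G minimum).
- Illustrative result: 4 disagreements in 40, so agreement = 36/40 = 90% (exact 95% CI 76% to 97%).
- q, the share of the cohort extracted as tested. The protocol gives none, so 10%, 30% and 50% are assumed.
- For vaccination, q is set to the lowest and highest coverage assumptions in Section 6.2, 30% and 70%.

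**Formulas.** PPV is agreement in the tested group and NPV is agreement in the not-tested group.
- True share tested = q × PPV + (1 − q) × (1 − NPV)
- Share of true tests missed = (1 − q) × (1 − NPV) / true share tested

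**Testing: three results that all print as 90%**

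| Errors (not tested / tested group) | q = 10% | q = 30% | q = 50% |
|---|---|---|---|
| 4 / 0 (PPV 1, NPV 0.8) | 0.18/0.28 = 64% missed | 0.14/0.44 = 32% missed | 0.10/0.60 = 17% missed |
| 2 / 2 (PPV 0.9, NPV 0.9) | 0.09/0.18 = 50% missed | 0.07/0.34 = 21% missed | 0.05/0.50 = 10% missed |
| 0 / 4 (PPV 0.8, NPV 1) | 0% missed | 0% missed | 0% missed |

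Weighted to the cohort at q = 30%, agreement is 0.30 × 1 + 0.70 × 0.8 = 86% in the first row and 0.30 × 0.8 + 0.70 × 1 = 94% in the last. The quota-weighted figure is 90% in both.

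**Vaccination: true coverage behind the same 90%**
- q = 30%: 0.30 + 0.70 × 0.2 = 44% if all errors are missed doses; 0.30 × 0.8 = 24% if all are false doses.
- q = 70%: 0.70 + 0.30 × 0.2 = 76%, or 0.70 × 0.8 = 56%.

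**Setting.** The 40 testing charts are 20 inpatient and 20 outpatient in the example. A pooled 36/40 can be 20/20 against 16/20, or 18/20 in each. Table 2 does not show which.

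**Precision once split.** Exact 95% CIs are 83% to 100% for 20/20 and 56% to 94% for 16/20. Fisher's exact test for that contrast gives p = 0.11. A fully crossed cell with 5/5 agreement has an interval of 48% to 100%.

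**The case against.** The best defense is that this is a template and not an analysis. The appendix offers suggestions, the tables are examples, the notes column could record the direction of disagreement, and nothing states that results go unweighted. Weighting and intervals can be left to a statistical analysis plan. Section 7.4 also checks for under-capture in other ways: it compares extracted proportions tested and vaccinated with source data and with outside figures, and calls for re-extraction when errors are found. Sites with validation data from earlier vaccination studies may skip the vaccination groups.

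Most of this stands and limits the point. It does not remove it: Table 2 is the only reporting format sites receive, it drops the groups the sampling creates, and a comparison of proportions does not show how individual records are misclassified.

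A reader might go further in three ways that the protocol does not support.
- *That Objective 3's inpatient–outpatient comparison cannot be made.* Most of Objective 3 concerns who is tested, by which test and in which setting, and it uses extracted data. Only the comparison of extraction accuracy by setting is lost, and only from Table 2 as drawn.
- *That the pooling is irreversible.* Sites keep the identifier key and their linked database (Section 7.3), so they can re-tabulate their own charts. Only someone who holds the tables alone cannot.
- *That a 90% result means about a third of tests are missed.* That requires an extracted testing share near 30% and every error in one group.

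**Conclusion.** The point holds as a weakness of the reporting template that should be corrected. Followed as drawn, Table 2 yields a number that estimates neither cohort accuracy nor sensitivity and does not tell missed records from false ones, which is what the accuracy items of Objectives 2 and 3 need.

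The size depends on assumptions. For testing, between 0% and 64% of true tests could be missed behind the same 90%, over assumed extracted shares of 10% to 50%. For vaccination, true coverage differs by 20 percentage points between the two extremes at either coverage value. These figures take 20 + 20 charts per element and, at the extremes, all four errors in one group; they illustrate and do not predict. That results would be unweighted is inferred from the table layout, since the text is silent.

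**What to change.** - **Table 2:** report the vaccination and testing rows separately by extracted status, with extracted-by-chart 2x2 counts and exact 95% confidence intervals. Show child/adult splits for both, and inpatient/outpatient splits for testing only, as marginal splits and not fully crossed cells. Do not ask for vaccination by setting, because that sample is not drawn by setting.
- **Denominators:** state that each of these elements is based on the charts sampled for it.
- **Table 1:** add the four sampling groups.
- **Coordinating center:** weight each group by its size in the cohort and report sensitivity and specificity, mainly at network level.

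The cost is a table layout and a short weighting step; no further charts are reviewed. The downside is that wider intervals replace one reassuring percentage, and comparisons by setting within one site stay imprecise.
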